12.4.2. Treatment and LPS Emergent Flag for Adverse Events

The flag assigned to a participant's AE will depend upon the type of AE, the magnitude of the AE and the study phase the AE occurred in. Each adverse event will be considered on a case-by-case basis.

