## 7. TREATMENTS

Study treatment is defined as any investigational treatment(s), marketed product(s), placebo, or medical device(s) intended to be administered to a study participant according to the study protocol.

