### 7.1. Treatments Administered

Study Treatment Name:	GSK2798745	Matching Placebo	Challenge Agent: GMP grade lipopolysaccharide from Escherichia coli (E. Coli Group 0113:H10:K Negative) for the segmental LPS challenge
Dosage formulation:	White to slightly coloured, round biconvex tablet. Product: AP, Tab-A	White to slightly coloured, round biconvex tablet. Product code: CET, Tab-A..	LPS is available from stock lyophilized in a 1 microgram vial, formulated in 1% lactose and 0.1% PEG6000. Clear solution.
Unit dose strength(s)/Dosage level(s):	Unit dose strength 2.4 mg. Dosage Levels: 4.8 mg and 2.4 mg	Not applicable	4 ng/kg
Route of Administration	Oral	Oral	Direct application to the lung segment, via bronchoscopy
Dosing instructions:	Two tablets to be taken on the morning of Day 1, then one tablet to be taken 12 hours later.	Two tablets to be taken on the morning of Day 1, then one tablet to be taken 12 hours later.	One single instillation of 10 mL by bronchoscopy 2 hours after dosing with GSK2798745 or placebo on Day 1.

Study Treatment Name:	GSK2798745	Matching Placebo	Challenge Agent: GMP grade lipopolysaccharide from Escherichia coli (E. Coli Group 0113:H10:K Negative) for the segmental LPS challenge
Packaging and Labeling	GSK2798745 tablets will be provided in high-density polyethylene (HDPE) bottles with child-resistant closures that include induction-seal liners. Each bottle will be labelled as required per country requirement.	Placebo tablets will be provided in high-density polyethylene (HDPE) bottles with child-resistant closures that include induction-seal liners. Each bottle will be labelled as required per country requirement.	-
Manufacturer	GSK	GSK	List Laboratories, Inc.

Sterile saline (0.9%) for control challenge will be sourced by the clinical site.

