**Assessment of Causality**

- The investigator is obligated to assess the relationship between study treatment and each occurrence of each AE/SAE.
- A "reasonable possibility" of a relationship conveys that there are facts, evidence, and/or arguments to suggest a causal relationship, rather than a relationship cannot be ruled out.
- The investigator will use clinical judgment to determine the relationship.
- Alternative causes, such as underlying disease(s), concomitant therapy, and other risk factors, as well as the temporal relationship of the event to study treatment administration will be considered and investigated.
- The investigator will also consult the Investigator's Brochure (IB) and/or Product Information, for marketed products, in his/her assessment.
- For each AE/SAE, the investigator **must** document in the medical notes that he/she has reviewed the AE/SAE and has provided an assessment of causality.
- There may be situations in which an SAE has occurred and the investigator has minimal information to include in the initial report to GSK. However, **it is very important that the investigator always make an assessment of causality for every event before the initial transmission of the SAE data to GSK.**
- The investigator may change his/her opinion of causality in light of follow-up information and send an SAE follow-up report with the updated causality assessment.
- The causality assessment is one of the criteria used when determining regulatory reporting requirements.

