12.4. Appendix 4: Study Phases and Treatment Emergent Adverse Events

12.4.1. Study Phases

Assessments and events will be classified according to the time of occurrence relative to the two study treatment doses and LPS/saline challenges.

Study Phase	Definition
Pre-Treatment	Date/Time \leq Study Treatment Start Date/Time
Post-Treatment	Study Treatment Start Date/Time $<$ Date/Time

NOTES:

- Study Treatment Start relates to the 1st dose received by the individual.

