12.11.7. Safety Tables

Safety: Tables					
No.	Population	IDSL / Example Shell	Title	Programming Notes	Deliverable [Priority]
Adverse Events (AEs)					
3.1.	All Subjects	AE1	Summary of All Adverse Events by System Organ Class and Preferred Term	ICH E3	SAC [1]
3.2.	All Subjects	AE1	Summary All Drug-Related Adverse Events by System Organ Class and Preferred Term/by Overall Frequency	ICH E3	SAC [1]
Serious and Other Significant Adverse Events					
3.3.	All Subjects	AE16	Summary of Serious Adverse Events by System Organ Class and Preferred Term (Number of Participants and Occurrences)	FDAAA, EudraCT	SAC [1]
3.4.	All Subjects	AE1	Summary of Adverse Events Leading to Permanent Discontinuation of Study Treatment or Withdrawal from Study by System Organ Class and Preferred Term	IDSL	SAC [1]
Laboratory: Chemistry					
3.5.	All Subjects	LB1	Summary of Chemistry Changes from Baseline	ICH E3	SAC [1]
Laboratory: Haematology					
3.6.	All Subjects	LB1	Summary of Haematology Changes from Baseline	ICH E3	SAC [1]
Laboratory: Urinalysis					
3.7.	All Subjects	LB1	Summary of Urine Concentration Changes from Baseline	ICH E3	SAC [1]
3.8.	All Subjects	UR3	Summary of Urinalysis Dipstick Results	ICH E3	SAC [1]
Laboratory: Hepatobiliary (Liver)					
3.9.	All Subjects	LIVER1	Summary of Liver Monitoring/Stopping Event Reporting	IDSL	SAC [1]

Safety: Tables					
No.	Population	IDSL / Example Shell	Title	Programming Notes	Deliverable [Priority]
ECG					
3.10.	All Subjects	EG1	Summary of ECG Findings	IDSL	SAC [1]
3.11.	All Subjects	EG2	Summary of Change from Baseline in ECG Values by Visit	IDSL	SAC [1]
3.12.	All Subjects	SAFE_T4	Summary of Number of Participants with Maximum ECG Values Meeting or Exceeding Pre-Specified Ranges of Concern by Category, Treatment and Timepoint.		SAC [1]
Vital Signs					
3.13.	All Subjects	VS1	Summary of Change from Baseline in Vital Signs	ICH E3 Include body temperature, heart rate, blood pressure.	SAC [1]
Columbia Suicide Severity Rating Scale (C-SSRS)					
3.14.	All Subjects	CSSRS1 (SAFE_T1)	Summary of C-SSRS Suicidal Ideation or Behaviour	Include Placebo column.	SAC [1]
Laboratory: Other					
3.15.	All Subjects	SAFE_T2	Summary of Faecal Occult Blood Test (FOBT) Data		SAC [1]
3.16.	All Subjects	LB1	Summary of Cardiac Troponin (cTn) Changes from Baseline		SAC [1]
3.17.	All Subjects	LB1	Summary of Coagulation Profile Changes from Baseline		SAC [1]
Spirometry					
3.18.	All Subjects	SAFE_T3	Summary of Spirometry Data		SAC [1]

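### A single causality judgement against an ambiguous *study treatment* can put LPS reactions into the drug-related AE table, and the treatment/LPS-emergent flag has no rule

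*SAP*

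**What the plan says.** **Causality.** Protocol Appendix 4 states: "The investigator is obligated to assess the relationship between study treatment and each occurrence of each AE/SAE". Protocol Section 7 defines the object of that judgement broadly: "Study treatment is defined as any investigational treatment(s), marketed product(s), placebo, or medical device(s) intended to be administered to a study participant". The Section 7.1 table, whose first row gives study treatment names, has GSK2798745, matching placebo and a third column that begins "Challenge Agent: GMP grade lipopolysaccharide from" *E. coli*. Other passages use *study treatment* for the tablets: Protocol Section 5.1 times its second dose from the LPS challenge, and SAP Section 12.6.2 defines treatment compliance and challenge compliance separately. The halt rule in Protocol Section 8.3 is worded on the investigational product.

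**Reporting.** SAP Section 12.11.7 lists Table 3.1 for all adverse events and Table 3.2 as "Summary All Drug-Related Adverse Events by System Organ Class and Preferred Term/by Overall Frequency". No rule says how an event attributed to the challenge enters Table 3.2.

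**Phases and flag.** SAP Section 12.4.1 opens: "Assessments and events will be classified according to the time of occurrence relative to the two study treatment doses and LPS/saline challenges". Its table then has two phases only, before and after treatment start, and a note adds: "Study Treatment Start relates to the 1st dose received by the individual". SAP Section 12.4.2 covers a treatment and LPS emergent flag: "The flag assigned to a participant's AE will depend upon the type of AE, the magnitude of the AE and the study phase the AE" falls into. It continues: "Each adverse event will be considered on a case-by-case basis". It names no assessor and does not mention blinding.

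**The concern.** Safety of GSK2798745 in LPS-challenged volunteers is a secondary objective, and Protocol Section 10.3.2 says safety data will not be formally tested. Readers will therefore rely on labels such as *drug-related*. The protocol's risk table expects pleuritic pain, pyrexia, headache and nausea after segmental LPS, and cough and transient fever after bronchoscopy. If one investigator treats LPS as a study treatment and another does not, the same fever is drug-related in one record and unrelated in the next. Table 3.2 then cannot be read as a statement about GSK2798745.

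The flag has a similar weakness. Once every event after the first dose falls in one phase, phase cannot distinguish a treatment-emergent from an LPS-emergent event. What is left is type and magnitude, weighed event by event by a person the SAP does not name.

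**Working it through.** The plan states no figure on this point, so there is none to reproduce. The check sets the passages side by side, then sizes the overlap.

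**1. What *study treatment* covers.**
- Protocol 7 and the 7.1 table: the LPS challenge agent is included on a literal reading.
- Protocol 5.1, the separate dosing and challenge rows of the schedule of activities, and SAP 12.6.2: tablets only.
- Protocol 8.3: investigational product.
- Protocol 9.5: AEs related to the study treatment or to the study.
- Appendix 4, electronic SAE reporting: relationship to IP or study participation.

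The causality instruction in Appendix 4 uses the term with two meanings, and the halt rule uses a different term.

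**2. Whether the phases can separate challenge events.** SAP 12.4.1 announces classification relative to the challenges but anchors only on the first dose. Everything after that dose is post-treatment.

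**3. How much of the AE window precedes LPS.** Inputs: challenge at 2 h (Protocol 9.2); AEs collected from start of treatment to the follow-up visit (Protocol 9.5.1), on Day 8 ± 1 day, which is nominally 7 × 24 = 168 h, range 144 to 192 h.
- 2/168 = 1.2%; range 2/192 = 1.0% to 2/144 = 1.4%.

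About 99% of the window follows LPS.

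**4. Effect on Table 3.2 (assumed rates; the documents give none).** Let d be the risk of a drug-caused AE on GSK2798745 and q the risk, equal in both arms, of a challenge AE recorded as drug-related. Taking the two as independent:
- GSK2798745: 1 − (1 − d)(1 − q). Placebo: q. Difference: d(1 − q).
- Example, d = 20% and q = 30%: 1 − 0.8 × 0.7 = 44% against 30%; difference 0.20 × 0.70 = 14 points.

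For d = 20% and 30 per arm, with nominal power for a two-sided 5% comparison of proportions (normal approximation, rough when placebo is at 0%):

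| q | GSK2798745 | Placebo | Difference | Nominal power |
|---|---|---|---|---|
| 0% | 20% | 0% | 20 points | 74.5% |
| 10% | 28% | 10% | 18 points | 42.5% |
| 30% | 44% | 30% | 14 points | 19.9% |
| 50% | 60% | 50% | 10 points | 11.8% |
| 70% | 76% | 70% | 6 points | 7.5% |

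Over the same range of q, the difference falls from 10 to 3 points for d = 10%, and from 30 to 9 points for d = 30%. With d = 0 both arms show q and the difference is zero. No safety test is planned, so the power column only gauges loss of sensitivity.

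**The case against.** The strongest reply is that the operational text is clear enough. The LPS column is itself labelled as a challenge agent, Protocol Section 7.2 treats challenge agents separately, the blinded supply in Section 7.3 can only be the tablets, and Section 9.5.1 names study treatment and mandated procedures separately. Appendix 4 tells the investigator to weigh alternative causes and timing, which is where a known LPS reaction belongs. The investigator is blinded, allocation is 1:1, and both arms receive LPS. Much of this stands. A reader might infer that a site must record a plain LPS fever as related; the documents support only that it may.

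Two further replies also stand. Magnitude has some place in defining emergence, because the protocol counts exacerbation and increased intensity as adverse events, so a rule on onset alone would be too narrow. And with LPS only 2 h after the first dose, a challenge phase will separate few events.

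The CRF is not among the documents. It may already have separate causality fields, but neither document asks for them.

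None of this supplies a rule for entering a challenge-attributed event in Table 3.2, the missing challenge phase, or an assessor and blinding status for the flag.

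**Conclusion.** The point holds as a defect of definition and reporting. Challenge reactions may be recorded as related to *study treatment* and so enter the descriptive Table 3.2. That would inflate the percentages in both arms and shrink any drug contrast by the factor (1 − q). How far depends on the LPS event rate and on how sites read the term; the documents give neither, so the table of assumed rates shows a range, not a forecast.

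Stronger readings are not supported:
- A reader might infer that a drug-related AE endpoint is compromised. The endpoint is adverse events overall; Table 3.2 is a display, and Table 3.1 does not depend on attribution.
- A reader might infer a spurious difference between arms. With LPS in both arms and a blinded investigator, none is expected.
- A reader might infer that the case-by-case flag drives Table 3.2, or is set by people who hold the codes. No listed AE display names the flag, and the title of Table 3.2 points to causality. The SAP does not say who sets the flag; the gap is that it does not require this to be done blind.

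No sample size or efficacy figure is affected.

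**What to change.** 1. In Protocol Appendix 4 and on the CRF, record relationship separately for GSK2798745/placebo, for the LPS/saline challenge and for bronchoscopy/BAL. Base SAP Table 3.2 on the first field only. This change does most of the work.
2. In SAP 12.4.1, add a phase anchored on the challenge: before treatment, first dose to challenge, after challenge.
3. In SAP 12.4.2, replace the case-by-case flag by a rule on time of onset or worsening. Name who applies it, require that it be applied without knowledge of treatment, and say which displays use it.
4. Reconcile *study treatment* and *investigational product* across Protocol Sections 7, 7.1, 8.3 and 9.5, Appendix 4 and the SAP. The term the halt rule should carry is for the sponsor and investigator to settle.

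Cost: a slightly longer AE page and revised wording. Dose times are already recorded (Protocol Section 7.6), and SAP 12.4.1 already assumes event dates and times; the challenge time is needed alongside them. Items 2 and 3 alone would separate few events because LPS follows the first dose by only 2 h. No dose, procedure or sample size changes.

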12.5. Appendix 5: Data Display Standards & Handling Conventions

12.5.1. Reporting Process

Software			

 The currently supported versions of SAS software and R will be used. 			
Reporting Area			
HARP Server	: UK1SALX00175.corpnet2.com		
HARP Compound	: \ARPROD\GSK2798745\207464\Internal_01 : \ARPROD\GSK2798745\207464\Internal_02 : \ARPROD\GSK2798745\207464\Headline : \ARPROD\ GSK2798745\207464\Final		
Analysis Datasets			

 Analysis datasets will be created according to legacy GSK A&R dataset standards. 			
Intermediate Datasets			

 The following instructions are recommended to make modelling and tracking of statistical analyses results easier. The Bayesian framework necessitates the storage of intermediate outputs datasets (convention dictates that they be stored in the dddata folder of the reporting effort). It is strongly recommended that a file naming convention be adopted across all MCMC analyses to allow easy grouping/location of associated items. The naming convention has to follow the SAS dataset length rules, and any HARP naming conventions. The file name is made up of components joined by underscores. This should allow items to automatically group/sort when viewed as a list. The components of the file name may change and is included for guidance. 			
Component ID	Description	Examples	Clarification
1	Three letters for the sample matrix	BAL BLD	Bronchoalveolar Lavage Blood
2	Item/Analyte	TPRO TNEU DNEU TALB <Bicat code>	Total Protein Total Neutrophil Count Differential Neutrophil Count Total Albumin Count <Taken from SI dataset >
3	Single digit Population code	1 2 etc	All Subjects Evaluable (Statistician will need to track assignments)

Component ID	Description	Examples	Clarification
4	Single digit Model ID (may vary depending on the analysis, so model 1 can have different meanings across objectives/sample matrices/endpoints)	1 2 etc	Primary Analysis Sensitivity Analysis 1 (Statistician will need to track assignments on a per objectives/sample matrices/endpoint basis)
5	Double digit Analysis ID (specific to the model)	01 02 03 04 etc	Statistician will need to track on a per item basis
6	MCMC related item	poall pokdein + Others as required	Posterior Summary Stats (processed and ready for display) Posterior samples

- Example for the output dataset produced from PROC MCMC with summary statistics used for T/L/F for the Primary analysis of 26h BAL Total Protein using the Evaluable population using the simplest model (only intercept, baseline and treatment group as covariates):
“BAL_TPRO_3_1_01_poall”

Generation of RTF Files

- RTF files will be generated for the final reporting effort.

12.5.2. Reporting Standards

General

 • The current GSK Integrated Data Standards Library (IDSL) will be applied for reporting, unless otherwise stated (IDSL Standards Location: https://spope.gsk.com/sites/IDSLLibrary/SitePages/Home.aspx): 
 • 4.03 to 4.23: General Principles • 5.01 to 5.08: Principles Related to Data Listings • 6.01 to 6.11: Principles Related to Summary Tables • 7.01 to 7.13: Principles Related to Graphics • Do not include participant level listings in the main body of the GSK Clinical Study Report. All participant level listings should be located in the modular appendices as ICH or non-ICH listings
Formats

 • GSK IDSL Statistical Principles (5.03 & 6.06.3) for decimal places (DP's) will be adopted for reporting of data based on the raw data collected, unless otherwise stated. • Numeric data will be reported at the precision collected on the eCRF. • The reported precision from non eCRF sources will follow the IDSL statistical principles but may be adjusted to a clinically interpretable number of DP's.
Planned and Actual Time

 • Reporting for tables, figures and formal statistical analyses: 
 • Planned time relative to dosing will be used in figures, summaries, statistical analyses and

calculation of any derived parameters, unless otherwise stated.
 
 The impact of any major deviation from the planned assessment times and/or scheduled visit days on the analyses and interpretation of the results will be assessed as appropriate. 
 Reporting for Data Listings: 
 Planned and actual time relative to study drug dosing will be shown in listings (Refer to IDSL Statistical Principle 5.05.1). Unscheduled or unplanned readings will be presented within the participant's listings. 																									
Unscheduled Visits																									

 Unscheduled visits will not be included in summary tables and/or figures. All unscheduled visits will be included in listings. 																									
Descriptive Summary Statistics																									
Continuous Data	Refer to IDSL Statistical Principle 6.06.1																								
Categorical Data	N, n, frequency, %																								
Graphical Displays																									

 Refer to IDSL Statistical Principles 7.01 to 7.13. Where appropriate, specific SAS attribute maps and formats should be applied to treatments groups or subjects to allow standardisation of graphics. Specific subject level attributes allow tracking and distinguishing subjects across displays and aids interpretation. Please consult with GSK statistician to obtain final attributes map. Treatment attributes: 
  
 Treatment	Colour	Plotting Symbol	Line Style	
   
 Placebo	Blue	Circle, Solid	Solid	
 
 GSK2798745	Red	Triangle (up), Solid	Solid	
  
 Example of subject attributes: 
  
 Subject	Colour	Plotting Symbol	Line Style	
   
 PPD	Cyan	Diamond (filled)	Solid	
 
 	Salmon	Asterisk	Dashed	
  
 		Treatment	Colour	Plotting Symbol	Line Style	Placebo	Blue	Circle, Solid	Solid	GSK2798745	Red	Triangle (up), Solid	Solid	Subject	Colour	Plotting Symbol	Line Style	PPD	Cyan	Diamond (filled)	Solid		Salmon	Asterisk	Dashed
Treatment	Colour	Plotting Symbol	Line Style																						
Placebo	Blue	Circle, Solid	Solid																						
GSK2798745	Red	Triangle (up), Solid	Solid																						
Subject	Colour	Plotting Symbol	Line Style																						
PPD	Cyan	Diamond (filled)	Solid																						
	Salmon	Asterisk	Dashed																						

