## 9. STUDY ASSESSMENTS AND PROCEDURES

- Study procedures and their timing are summarized in the [Schedule of Activities \(SoA\)](#).
- Protocol waivers or exemptions are not allowed.
- Immediate safety concerns should be discussed with the sponsor immediately upon occurrence or awareness to determine if the participant should continue or discontinue study treatment.
- Adherence to the study design requirements, including those specified in the SoA, is essential and required for study conduct.
- All screening evaluations must be completed and reviewed to confirm that potential participants meet all eligibility criteria. The investigator will maintain a screening log to record details of all participants screened and to confirm eligibility or record reasons for screening failure, as applicable.
- Procedures conducted as part of the participant's routine clinical management (eg, blood count) and obtained before signing of ICF may be utilized for screening or baseline purposes provided the procedure met the protocol-specified criteria and was performed within the time frame defined in the SoA.
- The maximum amount of blood collected from each participant over the duration of the study, including any extra assessments that may be required, will not exceed 500 mL.
- Repeat or unscheduled samples may be taken for safety reasons or for technical issues with the samples.

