12.6. Appendix 6: Derived and Transformed Data

12.6.1. General

Multiple Measurements at One Analysis Time Point

 • Mean of the measurements will be calculated and used in any derivation of summary statistics but if listed, all data will be presented. • If there are two values within a time window (as per Section 12.3.1) the value closest to the target day for that window will be used. If values are the same distance from the target, then the mean will be taken. • Participants having both High and Low values for Normal Ranges at any post-baseline visit for safety parameters will be counted in both the High and Low categories of “Any visit post-baseline” row of related summary tables. This will also be applicable to relevant Potential Clinical Importance summary tables.
Study Day

 • Calculated as the number of days from First Dose Date: 
 • Ref Date = Missing → Study Day = Missing • Ref Date < First Dose Date → Study Day = Ref Date – First Dose Date • Ref Date ≥ First Dose Date → Study Day = Ref Date – (First Dose Date) + 1

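### The SAP keeps unscheduled visits out of every summary table, so the maximum-ECG count and any any-visit-post-baseline row would cover scheduled assessments only

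*SAP*

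**What the plan says.** SAP 12.5.2 has a short rule on unscheduled visits: "Unscheduled visits will not be included in summary tables and/or figures". Its companion sentence sends them elsewhere: "All unscheduled visits will be included in listings". Under the heading for data listings, the same section adds: "Unscheduled or unplanned readings will be presented within the participant's listings". It also says that summaries use planned time relative to dosing unless otherwise stated. It makes no exception for displays of extremes.

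Two other parts of the SAP describe summaries of extremes.

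- Section 12.11.7 lists Table 3.12, titled "Summary of Number of Participants with Maximum ECG Values Meeting or Exceeding Pre-Specified Ranges of Concern by Category, Treatment and Timepoint". It has no programming note.
- Section 12.6.1 says that participants with both high and low values at some post-baseline visit "will be counted in both the High and Low categories of “Any visit post-baseline” row of related summary tables", and continues: "This will also be applicable to relevant Potential Clinical Importance summary tables".

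Protocol section 9 expects extra readings: "Repeat or unscheduled samples may be taken for safety reasons or for technical issues with the samples". Protocol 9.7.4 mentions that additional QTc readings may be needed, and 8.1.3.2 calls for clinically appropriate testing of a participant with symptoms of cardiac ischaemia.

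**The concern.** Leaving unscheduled visits out of by-timepoint means is ordinary practice, because they have no common nominal time and would distort those rows. A count of maxima, or of values at any visit, asks a different question: did this participant ever cross the threshold? For that question a reading taken because something happened is among the most informative, and a blanket exclusion removes it.

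What is at stake is the comparison by arm. Safety and tolerability is a secondary objective, and ECG and laboratory assessments are among its endpoints. An ECG value in a range of concern that was seen only on an unscheduled tracing would be absent from the table meant to count such values. SAP 12.5.2 also keeps participant-level listings out of the main body of the study report, so a reader who relies on the tables there could see a lower count than the data support.

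**Working it through.** The plan gives no figure to reproduce. The check sets the provisions side by side and then counts scheduled ECGs.

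**1. Does any provision bring unscheduled readings back into Table 3.12?** The 12.5.2 exclusion has no carve-out, and the Table 3.12 entry has no note. SAP 12.7.1 keeps withdrawal visits, either slotted to a window or summarised as such, and includes planned data from withdrawn participants. It does not mention the unscheduled reading that led to a withdrawal. SAP 12.6.1 averages multiple measurements at one analysis time point, or takes the value closest to target within a window. However, the window section it cites (12.3.1) refers to the Study Reference Manual and itself specifies only the 26 h PK sample. A repeat near a nominal time might therefore enter, possibly averaged. A reading far from any nominal time has no stated route.

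**2. Are 12.5.2 and 12.6.1 consistent?** Section 12.6.1 speaks of any post-baseline visit. Section 12.5.2 says that some post-baseline visits never enter a table. Nothing says which prevails, so the programmer would have to choose.

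**3. Which ECGs are scheduled after dosing?** From the schedule of activities (protocol 2.2 and 2.3, repeated in SAP 12.2.3 and 12.2.4):

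| Time after first dose | Event | Scheduled ECG |
|---|---|---|
| 0 h | First dose (median Tmax 1.5 h, protocol 5.4) | None after dosing |
| 2 h | Bronchoscopy, baseline BAL, LPS and saline challenge | None |
| 12 h | Second dose | None |
| 26 h | Second bronchoscopy and BAL | None |
| 30 h | Before discharge | One, single |
| Day 8 (±1 day) | Follow-up | One, single |

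Scheduled post-dose ECGs per participant: 1 + 1 = 2. None falls between the first dose and 30 h.

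**4. Follow one hypothetical case.** Suppose an ECG prompted by symptoms at some time between 0 h and 30 h shows a QTc above 500 msec, the limit in SAP 12.8.2, and the two scheduled tracings are below it. The values would appear in Listings 27 and 28. Under 12.5.2 as written, Table 3.12 would use only the 30 h and Day 8 tracings, so the participant would not be counted.

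**5. Size of one such case.**

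- With 30 in the arm: 1/30 = 3.3%, against 0/30 = 0% as tabulated.
- If the study stopped with about 20 per arm: 1/20 = 5.0%, against 0%.
- If it stopped with about 10 per arm: 1/10 = 10%, against 0%.

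These figures show the effect of one event. They are not an expected rate, because the documents do not say how often unscheduled extremes would occur.

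**The case against.** The case against is substantial, and much of it stands.

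- **Visits are not readings.** The exclusion is headed as a rule on visits, and the sentence on unplanned readings says what listings contain. Before 30 h participants are resident on site, so an extra ECG is not plainly an unscheduled visit. This stands as an ambiguity. It does not remove the point, because no text gives such a reading a place in a table either.
- **Table 3.12 is by timepoint.** Its title says so, and its shell is not available, so an overall-maximum row cannot be confirmed. This stands, and the wording of the fix allows for it.
- **Laboratory tables.** A reader might infer that laboratory extremes would be counted as zero in a summary of values of potential clinical importance. No such laboratory summary is listed: Tables 3.5, 3.6, 3.7, 3.16 and 3.17 are changes from baseline, 3.8 is dipstick results, and flagged laboratory values go to Listings 23, 24 and 26.
- **Tables 3.9 and 3.10.** A reader might extend the point to these. The first summarises liver event reporting, for which the protocol has a dedicated form. The second is titled only as ECG findings. Neither is shown to be affected.
- **Other routes.** QTcF above 500 msec requires withdrawal under protocol 8.1.2, so that participant reaches disposition Table 1.1. Findings judged clinically significant are adverse events and reach Table 3.1, and Table 3.4 if they lead to withdrawal. This stands for those cases. It does not cover a value that crosses a threshold without being judged clinically significant. For instance, SAP 12.8.2 sets PR and QRS limits that have no withdrawal rule in protocol 8.1.2.
- **Repeats after an abnormal scheduled value.** The first value is already eligible for the table, so leaving out the repeat need not hide the abnormality.

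**Conclusion.** The point holds as a gap in safety reporting. SAP 12.5.2, followed as written, conflicts with the SAP's own summaries of extremes and can understate them: Table 3.12 for ECGs, and any table that uses the 12.6.1 row. The effect is 3.3 percentage points per missed participant in an arm of 30, with an unknown number of such participants.

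The conclusion assumes that an unscheduled reading is handled like an unscheduled visit, and that Table 3.12 carries, or is read as giving, a participant-level maximum. The available text does not settle either.

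A reader might go further and infer that every finding between dosing and 30 h is lost. The documents do not support that. The absence of a scheduled ECG in that period is a feature of the schedule, not an effect of the reporting rule, and the readings remain in the listings. No formal safety hypothesis is tested, and the primary analysis and interim rules are untouched. The change should be made, but it is not critical to the trial.

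**What to change.** In SAP 12.5.2, limit the exclusion of unscheduled visits to by-timepoint summaries. Add one sentence stating that any maximum or any-visit-post-baseline row, in Table 3.12 and in any table that uses the 12.6.1 row, includes unscheduled and repeat post-baseline readings. It should say explicitly that this covers readings taken during the inpatient stay. One way to do it is to add a row to Table 3.12 for any time post-baseline, including unscheduled.

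Keep the by-timepoint rows beside it. A row that includes unscheduled readings gives more chances of an extreme to participants who were measured more often, so the scheduled-only rows remain the like-for-like comparison.

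The cost is one SAP sentence, one extra row and some programming. No data collection or clinical procedure changes. Settling it before unblinding avoids a choice made with the results in view.
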